### **Validation dataset**

After completion of the development phase, data of the following interventions will be used in the validation dataset. The validation dataset shall be used to assess the generalization performance of the model(s) developed during the development phase. When moving to the validation stage, all steps used from input data, i.e. individual impedance spectrums for each electrode pair, to the score prediction shall be fully determined. When moving to the validation phase the model(s) shall be locked, remaining unchanged during the course of the validation phase.

This same procedure of splitting the dataset into two sets (development dataset and validation dataset) will be performed for the primary performance endpoint assessment as well as for the secondary and tertiary endpoint assessments.

Confidence intervals will be computed with the bootstrap.

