## Clinical investigation plan - CLOT OUT

## 5 STUDY SUMMARY

Title	CLOT OUT (Clotild® Smart Guidewire System evaluation in Endovascular Thrombectomy procedure)
Protocol Number	SEN_CLOTILD_FIH_1
Study Device	Clotild® Smart Guidewire System (CSGS)
Purpose	
The objective of the study device is to evaluate the safety and ability of Clotild® Smart Guidewire System to provide electrophysiological measurements.
 
The electrophysiological measurements will be used to update CSGS's database and thus improve the prediction accuracy of the model in providing physicians with insights for treating ischemic stroke.

Study type	First-In-Human
Study design	Prospective, Multicenter, Single-arm study
Number of patients and Clinical Sites	Up to 42 patients at up to five Australian and up to eight European Centres
Patient Population	
Subjects presenting with acute ischemic stroke due to an occlusion with origin in the M1 and eligible for EVT based on neuro-interventionist and/or neurologist investigators' opinion.
 
Up to 42 patients will be enrolled following an analysis of the data of the first 20 enrolled patients by a Data Safety Monitoring Board (DSMB) and its recommendation to proceed with the study. DSMB review is planned at 5 and 20 patients, all centers combined, and the final review after the last patient has been enrolled.

Endpoints	
PRIMARY ENDPOINTS
 
Primary Safety Endpoint
 
The Primary Safety Endpoint is defined as the proportion of patients having intracranial vessel perforation and / or dissection due to Clotild® Smart Guidewire usage at the site of usage in intracranial vessels.

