**15.4 ENDPOINT ANALYSIS****15.4.1 Primary Endpoint analysis**

For the **Primary Safety Endpoint** descriptive statistics will be provided showing the proportion of patients with intracranial vessel perforation and / or dissection due to Clotild® usage. Furthermore, a 95% confidence interval will be estimated. The primary safety endpoint will be determined in all patients in whom the guidewire went through the introduction sheath.

The **Primary Performance Endpoint** is defined as the ability to perform binary classification of individual electrophysiological parameter measurements (local scale) by distinguishing local regions with substantial red blood cell content (RBC-positive) from regions with negligible red blood cell

---

 *Good Machine Learning Practice for Medical Device Development: Guiding Principles (FDA, October 2021)*

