### Treated Population

All patients in which the guidewire went through the sheath, even though if not all eligibility criteria were met or if a device failure occurred or if the clot could not be retrieved.

The primary safety endpoint will be determined on the Treated Population.

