#### **iv. Statistical significance level**

A significance level of 0.05 will be used.

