#### **vi. Handling of missing data**

### **Missing CSGS data**

Data captured by the CSGS might be missing or anomalous. Based on the Device Deficiency rate obtained in the first 31 treated subjects, the estimated amount is 40%. This missingness/anomaly might be due to the following reasons:

1. Technical malfunctions, leading to missing data or anomalous data, among which:
  - device anomaly caused by manufacturing anomaly;

- device anomaly due to electrical connection loss during navigation.
2. Use error, leading to:
- missing data because measurements have not been tagged;
  - anomalous data because the sensor was covered by the microcatheter while the measurement was tagged, as confirmed by the imaging Core Lab on the angiography images corresponding to the tagged measurement.

The criteria to discard anomalous measurements due to technical malfunction include:

- Any acquisition associated with an error code raised by transmitter software (for instance due to loss of communication between sensor and transmitter) will be excluded.
- Electrophysiological measurement from an electrode pair that shows a constant raw digital signal across acquisition frequencies (constant or piecewise constant with a single step) is considered anomalous and will be excluded.
- Electrophysiological measurement from an electrode pair that shows digital saturation consistently from REFERENCE to PRE-CLOT is considered anomalous; all remaining measurements made with this electrode pair will be excluded.
- Anomalies related to invalid reference measurements are reported as too-high dispersion across electrode pairs in the 'REFERENCE' measurement. Persistence of the anomaly up to the 'PRE CLOT' measurement requires exclusion of all measurements from the concerned electrode pairs.

Since the underlying assumption is completely missing at random, no imputation will be done for missing clot data. To deal with missing data, an attrition rate is taken into account in the sample size calculation.

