## **xii. Safety analysis**

The primary safety endpoint (defined in 4) will be analysed in the Treated Population and presented in a table by means of descriptive statistics (count, percentages and 95% CI).

All Adverse Events will be classified with the Lowest Level Term (LLT) from the MedDRA dictionary (version 24.0, March 2021). All adverse events with onset during the study period will be displayed in summary tables for the ITT population. Tables will show the number of adverse events, the number and the percentage of patients affected by relation to usage of the device or the study procedure or to the EVT procedure (study procedure excluded) or underlying disease. Adverse events will be divided by seriousness. Severity, actions taken and outcome of the adverse events will be displayed in tables. Divisions will be made according to the timing of the event (during procedure, after procedure). All adverse events with descriptions of the event will be listed.

Technical events are defined as device or accessory malfunctions that are not associated with any clinical sequelae. All study site reported technical events will be summarized. The number and percentage of patients experiencing 1 or more technical events will be presented by the event description using counts and percentages. A detailed listing of a device deficiencies and malfunctions will be presented.

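### The primary safety proportion has no interval method of its own, and the only method the SAP names for analysing results, the bootstrap, gives 0% to 0% if no event is seen

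*SAP*

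**What the plan says.** Safety is the primary objective (Protocol 10.1, SAP 2), and Protocol 15.1 limits the primary safety analysis to description. The interval is requested in three places. Protocol 15.4.1 says "Furthermore, a 95% confidence interval will be estimated", SAP 4.a repeats this, and SAP 8.c.xii wants the endpoint "presented in a table by means of descriptive statistics (count, percentages and 95% CI". None of them names a method.

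The denominator is fixed in SAP 8.b: "The primary safety endpoint will be determined on the Treated Population", meaning patients in whom the guidewire passed through the sheath.

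One sentence in SAP 8.c.i (Statistical Procedures) names a method: "Confidence intervals will be computed with the bootstrap". Its wording has no restriction. It is, however, the last line of the Validation dataset subsection, which is about the prediction model: "The validation dataset shall be used to assess the generalization performance of the model(s) developed during the development phase". The bootstrap variant, number of resamples and resampling unit are not given.

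The Hanley and McNeil formula is the only other interval method in either document. It is used for the AUC in the sample-size calculation (Protocol 15.5, SAP 6), not for analysing results.

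**The concern.** A bootstrap draws new samples from the observed outcomes. If every treated patient is event-free, every resample is event-free too, and the interval has no width. For a rare complication in at most 42 patients, an event-free sample is a realistic case. A first-in-human report would then give a 95% interval of 0% to 0% for its primary safety endpoint, when the data could not exclude a rate of about 8%.

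If the bootstrap sentence is instead read as covering only model metrics, the safety interval has no method at all. It could then be chosen after the event count is known.

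**Working it through.** **Inputs**
- Largest possible n: 42 (Protocol 5, "Up to 42 patients at up to five Australian and up to eight European Centres").
- Smaller n as a range check: 31 (SAP 8.c.vi, "Based on the Device Deficiency rate obtained in the first 31 treated subjects, the estimated amount is 40"%).
- Level: two-sided 95% (SAP 8.c.iv, "A significance level of 0.05 will be used").
- Expected perforation or dissection rate: none stated. True rates of 1%, 2%, 3% and 5% below are assumptions.
- Patients are resampled independently (assumption; the SAP gives no unit).

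**The plan's own figure.** The documents state no safety interval to reproduce, but the ceiling of 42 can be checked. With A = 0.85, B1 = A/(2−A), B2 = 2A²/(1+A), the Hanley-McNeil variance is [A(1−A) + (n₁−1)(B1−A²) + (n₂−1)(B2−A²)]/(n₁n₂). With 14 × 3 × 5.44 = 228.5 measurements split 53/47, the width 2 × 1.96 × SE is 0.0994. With 13 interventions it is 0.1031. So 14 is the smallest number that meets the 0.1 limit, and (11 + 14)/0.60 = 41.7, rounded up to 42. The plan's figure reproduces.

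**Step 1: zero events.** With x events in n patients, the resampled count follows Binomial(n, x/n). At x = 0 it is always 0, so the percentile, basic and BCa variants all give 0% to 0%. The exact upper limit is 1 − 0.025^(1/n): 8.4% at n = 42 and 11.2% at n = 31. Wilson gives 8.4% and 11.0%.

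**Step 2: one or two observed events, n = 42.** Percentile limits are the 2.5% and 97.5% quantiles of Binomial(42, x/42), divided by 42. At x = 1 the cumulative probability is 0.922 at a count of 2 and 0.983 at 3, so the upper limit is 3/42 = 7.1%. At x = 2 it is 0.952 at 4 and 0.986 at 5, so the upper limit is 5/42 = 11.9%. Clopper-Pearson limits are Beta quantiles: 0.025 of Beta(x, n−x+1) and 0.975 of Beta(x+1, n−x).

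| Observed | Percentile | Basic | BCa | Clopper-Pearson | Wilson |
|---|---|---|---|---|---|
| 0/42 | 0–0% | 0–0% | 0–0% | 0–8.4% | 0–8.4% |
| 1/42 | 0–7.1% | 0–4.8% | 0–11.9% | 0.1–12.6% | 0.4–12.3% |
| 2/42 | 0–11.9% | 0–9.5% | 0–16.7% | 0.6–16.2% | 1.3–15.8% |

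Resampling 20,000 times gave the same percentile limits.

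**Step 3: coverage over assumed true rates, n = 42.** Coverage is the sum of Binomial(42, p) probabilities over those counts whose interval contains p. At p = 1%, for example, the zero-event interval misses p and has probability 0.99^42 = 0.656, which leaves 0.344.

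| True rate | P(0 events) | Percentile | BCa | Clopper-Pearson |
|---|---|---|---|---|
| 1% | 66% | 34% | 34% | 99% |
| 2% | 43% | 56% | 52% | 99% |
| 3% | 28% | 72% | 71% | 99% |
| 5% | 12% | 88% | 88% | 98% |

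Most of the shortfall comes from the zero-event samples.

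**The case against.** The strongest objection is scope. All of SAP 8.c.i concerns prediction models. The sentence just before the bootstrap line refers to the primary performance, secondary and tertiary endpoints and does not mention safety. Safety has no validation dataset and is handled under separate headings that do not refer back to 8.c.i. The AUC, which does need an interval under SAP 4.b, is a natural target. This stands as far as it goes: a reader might infer that the SAP expressly prescribes the bootstrap for safety, and it does not. But the sentence has no restriction, and the narrow reading leaves the primary safety interval without any method. Either reading calls for the same correction.

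The variant also matters. The one- and two-event comparisons assume the percentile method. BCa upper limits there (11.9% and 16.7%) are close to the exact 12.6% and 16.2%. This stands too, but no variant tried avoids the collapse at zero.

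Finally, the practical harm is bounded. No hypothesis, performance goal or stopping rule uses the interval, and the count, adverse-event tables and listings would appear with it. This stands, and it limits the severity. The worst-case sensitivity analysis (SAP 8.c.xviii) is no answer: it changes how missing outcomes are counted, not the interval method, and does nothing if none are missing.

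**Conclusion.** The point holds as a gap in the specification that should be fixed. The primary safety interval has no stated method suited to it, and the one analysis method named fails if no event occurs: 0% to 0% against an exact 0% to 8.4% with 42 treated, or 0% to 11.2% with 31. At one or two observed events the understatement of the upper limit depends on the variant (7.1% against 12.6%, and 11.9% against 16.2%, for the percentile method).

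Three stronger readings are not supported:
- A reader might infer that an event-free result is to be expected. The documents give no rate, and the probability runs from 66% to 12% over the assumed range.
- A reader might infer that the bootstrap undercovers when one or two events are observed. Coverage belongs to a true rate, not a count. When one event in 42 is expected, percentile coverage is about 64%; when two are expected it is about 87%, a moderate shortfall.
- A reader might extend the defect to procedural success or the worst-case safety analysis. The documents ask for no interval on either.

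The figures assume independent patients and, unless stated, 42 treated. That is the enrolment ceiling, so the treated number may be lower.

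**What to change.** Before database lock:
- In SAP 4.a and 8.c.xii, state that the primary safety proportion is reported with a two-sided 95% exact (Clopper-Pearson) interval in the Treated Population. Wilson would also avoid the collapse; one method should be named.
- Use the same method for any other proportion that is reported with a confidence interval.
- In SAP 8.c.i, limit the bootstrap sentence to the model-performance metrics (the AUCs).

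The change takes a few words in three SAP sections and needs no new data and no change to the sample size. Protocol 15.1 already leaves detail to the SAP, and Protocol 15.4.1 names no method to contradict. The cost is a less favourable upper safety bound, for example 8.4% in place of 0% at 0/42.

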#### **ii. Listing and descriptive statistics**

All original and derived parameters as well as population characteristics will be described. Data will be described using summary statistics as described in the sections below. Frequency counts (number of subjects [n] and percentages) will be made for each qualitative variable. Descriptive statistics (n, mean, standard deviation [SD], median, minimum and maximum) will be calculated for each quantitative variable (unless otherwise stated). In general, all data will be listed, sorted by site and subject, and when appropriate by visit number within subject.

#### **iii. Rounding and decimal places**

P-values  $\geq 0.001$  will be reported to 3 decimal places; p-values less than 0.001 will be reported as " $<0.001$ ". The mean, standard deviation, and any other statistics other than quantiles, will be reported to one decimal place greater than the original data. Quantiles, such as median, or minimum and maximum will use the same number of decimal places as the original data. Estimated parameters, not on the same scale as raw observations (e.g. regression coefficients) will be reported to 3 significant figures.

#### **iv. Statistical significance level**

A significance level of 0.05 will be used.

#### **v. Software**

Statistical software packages like SAS, SPSS or R will be used.

#### **vi. Handling of missing data**

### **Missing CSGS data**

Data captured by the CSGS might be missing or anomalous. Based on the Device Deficiency rate obtained in the first 31 treated subjects, the estimated amount is 40%. This missingness/anomaly might be due to the following reasons:

1. Technical malfunctions, leading to missing data or anomalous data, among which:
  - device anomaly caused by manufacturing anomaly;

- device anomaly due to electrical connection loss during navigation.
2. Use error, leading to:
- missing data because measurements have not been tagged;
  - anomalous data because the sensor was covered by the microcatheter while the measurement was tagged, as confirmed by the imaging Core Lab on the angiography images corresponding to the tagged measurement.

The criteria to discard anomalous measurements due to technical malfunction include:

- Any acquisition associated with an error code raised by transmitter software (for instance due to loss of communication between sensor and transmitter) will be excluded.
- Electrophysiological measurement from an electrode pair that shows a constant raw digital signal across acquisition frequencies (constant or piecewise constant with a single step) is considered anomalous and will be excluded.
- Electrophysiological measurement from an electrode pair that shows digital saturation consistently from REFERENCE to PRE-CLOT is considered anomalous; all remaining measurements made with this electrode pair will be excluded.
- Anomalies related to invalid reference measurements are reported as too-high dispersion across electrode pairs in the 'REFERENCE' measurement. Persistence of the anomaly up to the 'PRE CLOT' measurement requires exclusion of all measurements from the concerned electrode pairs.

Since the underlying assumption is completely missing at random, no imputation will be done for missing clot data. To deal with missing data, an attrition rate is taken into account in the sample size calculation.

#### **Missing clot data (histological data)**

Clinical experience reports that roughly 40% of clots cannot be retrieved during the procedure. This will lead to missing data for histological assessment. However, over the first 31 treated subjects, 30 clots were collected and analyzed by the histology core lab, which is better than expected and decreases the impact of this potential missing data. Here as well, missingness completely at random is assumed and no imputation will be done for the missing clot data.

#### **Missing patient data**

Primary and secondary endpoint data are all captured during the procedure. Follow-up safety data are captured until 24 hours post-procedure. Missing patient data will be rare and assumed completely at random. No imputation of missing patient data will be performed.

#### **Missing and partial Adverse Event dates**

The recorded dates for adverse events are important for an accurate tabulation of both events and patients, and required for the following:

1. Defining the peri-procedural or post-procedural algorithm.
2. Designation of unique adverse event occurrences recorded intra-patient.

Completely missing or partially missing adverse event dates will be imputed as follows, after due diligence to obtain accurate adverse event information has failed:

If the adverse event start date is completely missing the adverse event will be considered as having occurred during the study unless it can be determined that the adverse event end date occurred prior to the start of the study procedure. If the adverse event end date can be established as prior to the date of the study procedure, the adverse event will be considered as having occurred prior to the start of the study.

If the adverse event start date is partially missing and the partial date is not sufficient to determine if the event occurred after the start of the study, then the adverse event will be considered as having occurred during the study.

#### **vii. Timing of the analysis and interim analysis**

Interim DSMB analyses are planned to be performed after treatment of the first 5 patients, 20 patients and after all patients have been enrolled. These interim analysis only include a safety analysis (see xii). Primary safety endpoint will be assessed as well as the amount, seriousness and severity of (S)AEs and their relationship to the study device, procedure and EVT and device deficiencies. This evaluation will be used by the DSMB to recommend to proceed with the study.

The DSMB could have advised for temporary enrolment suspension if one of the following events occur:

- subarachnoid hemorrhage and/or
- symptomatic intracranial hemorrhage

and further investigation is to be done to assess the severity and the causality to the device if:

- <5 patients were enrolled in the study: each event was to be evaluated by the DSMB chairman. The DSMB chairman had to give feedback within 48hrs to suspend enrolment to further investigate the event or not.
- >5 and <10 patients were enrolled in the study: the study enrolment was to be temporarily suspended if >2 events occurred since start of enrolment.
- >10 and <20 patients were enrolled in the study: the study enrolment was to be temporarily suspended if >4 events occurred since start of enrolment.

In order to develop the prediction model(s), data from the development dataset are analysed on an ongoing basis.

A final analysis of all study endpoints is planned after all patients left the study, all data is monitored, queried, and the database is locked.

#### **viii. Clinical investigation plan deviations**

A deviation from the clinical investigation plan is defined as an event where the clinical investigator or site personnel did not conduct the study according to the clinical investigation plan, ISO 14155:2020 and any national or local regulatory requirements.

Clinical investigation plan deviations are captured in the eCRF and will be listed in the final analysis and include all of the information recorded. This listing will be sorted by clinical site, patient number and the type of deviation. Clinical investigation plan deviations can impact the results of the analysis, therefore, reasons for clinical investigation plan deviations will be screened individually to check if bias could have resulted due to specific clinical investigation plan deviations as missed assessments.

A separate table will be presented for deviations to the in- and exclusion criteria and a detailed listing of patients not fulfilling in- or exclusion criteria will be provided.

#### **ix. Patient accounting and study disposition**

A complete accounting of patient participation in the study will be presented in a table entitled 'Patient accounting and final study disposition'. The purpose of this table is to provide an accounting of patients from their entrance into the study through the final visit and to account for the evaluations of patients in the analyses of performance and safety, including reasons for early study termination. The table will display the number and percentage of patients that:

- Were enrolled
- Underwent the study procedure
- Completed the 24 hours post-procedure evaluation
- Discontinued from the study
  - Withdrew Consent
  - Failure to meet inclusion and exclusion criteria
  - Substantial non-compliance
  - Physician decision
  - Adverse event
  - Lost to follow-up
  - Discontinuation by sponsor
  - Other (list exact reason)

This table will be presented by investigation site. The listing with reasons patients did not undergo the study procedure will contain the individual reason. A separate listing sorted by patient number will include the reason for withdraw for all patients who discontinue prematurely.

